6.4 Methods of statistical analyses

Statistical analysis will be carried out by, or under the guidance of, the biostatistical group at AstraZeneca using the SAS system, version 8.2. Pharmacokinetic analysis will be carried out by, or under the guidance of, the Pharmacokinetic Section, Experimental Medicine, at AstraZeneca.

Where standard descriptive statistics are referenced below, this will include the mean, standard deviation, median, minimum and maximum for continuous variables, and counts and frequency percentages for discrete variables.

Where treatment group is referenced, this will refer to the dosage regime being given at that time. Therefore, the following treatment groups will be referenced:

AZD6140 100 mg bid (Cohort A)

AZD6140 300 mg bid (Cohort B)

AZD6140 placebo (Cohorts A and B)

For reporting purposes, the AZD6140 placebo groups in Cohorts A and B will be combined.

(a) Demographic and baseline data

All demographic and baseline data, including medications, will be listed and summarized using standard descriptive statistics by group and ethnic group. No hypothesis test comparing groups will be made.

(b) Pharmacokinetics

Pharmacokinetic data (including plasma concentrations and summary parameters for both parent and metabolite) will be summarized and listed by treatment group and ethnic group. The plasma concentrations and pharmacokinetic parameters, except for $t_{1/2}$, t_{max} , and V_z/F , will be summarized using geometric mean, coefficient of variation (CV) and the standard descriptive statistics. $t_{1/2}$ and V_z/F will be summarized by standard descriptive statistics. t_{max} will be summarized using standard descriptive statistics except for (arithmetic) mean and standard deviation.

The primary pharmacokinetic parameters ($AUC_{ss,\tau}$, $C_{ss,max}$) with / without weight adjustment will be compared in a factorial design between the Japanese and Caucasian subjects adjusting for dose level if appropriate (no significant interaction between dose and ethnic group). Similarity in exposure between ethnic groups will be concluded if the 90% confidence interval for the ratio (Japanese/Caucasian) of geometric mean AZD6140 $AUC_{ss,\tau}$ and $C_{ss,max}$ are completely contained within the interval (0.7-1.43) for all comparisons. The comparison of these parameters with/without BMI adjustment might be considered.

(c) Bleeding time

Bleeding time data will be summarized and listed using standard descriptive statistics by treatment group and ethnic group. Graphical representations of the data will also be produced.

(d) Optical aggregometry data

Optical aggregometry data will be summarized by treatment group and ethnic group and listed, both as absolute values and as percentage inhibition, calculated from the formula given in section 4.3.1 of this protocol. Graphical representations of the data will also be produced.

(e) Adverse events

Adverse events will be summarized by System Organ Class and Preferred Term, using MedDRA by treatment group and ethnic group. All adverse event data will be listed for all subjects. Separate listings of all serious adverse events, deaths or other significant adverse events will be presented.

(f) Laboratory data

All laboratory safety data, incorporating hematology, clinical chemistry and urinalysis data and haemocult data for Japanese subjects will be listed, with deviations from the normal range explicitly noted on the listings.

Continuous laboratory data will be summarized using standard descriptive statistics. Both absolute values and change from pre-dose baseline will be summarized. In addition, shift plots will be produced for each variable. All summaries will be by treatment group and ethnic group.

Discrete laboratory data will be summarized using standard descriptive statistics. In addition, shift tables showing change from pre-dose baseline will be produced. All summaries will be by treatment group and ethnic group.

(g) 12-lead ECG data

Twelve-lead ECG data will be summarized and listed using standard summary statistics by treatment group and ethnic group. Both absolute values and change from pre-dose baseline will be summarized. In addition, mean plots showing change from within treatment group across time will be produced.

(h) Vital signs

Vital signs data will be summarized and listed using standard summary statistics by treatment group and ethnic group. Both absolute values and change from pre-dose baseline will be summarized. In addition, mean plots showing change within treatment group across time will be produced for absolute values.

(i) Physical examination

Physical examination abnormalities will be listed.

6.5 Determination of sample size

Each ethnic group-cohort (dose) arm of the study will include 18 subjects (15 active and 3 placebo). Seventy-two subjects will be randomized in total.

With 12 active evaluable subjects per arm in a factorial design $C_{ss, max}$ and $AUC_{ss, \tau}$ of AZD6140, the study has been planned to have at least 90% power to show that the 90% confidence limits for the ratio (Japanese/Caucasian) of geometric mean will fall within the interval 70% to 143%, if the hypothesis of equality is true assuming that there is no significant

interaction between dose and ethnic group. Based on a previous multiple ascending dose study in Caucasian subjects (Study No D5130C05239: In this study the estimates of CV ranged from 12% to 69% for C_{\max} and 26% to 54% for AUC_{τ} in 13 treatment groups. The mean CVs weighted by number of subjects in each treatment groups for C_{\max} and AUC_{τ} were 38.1% and 37.8%, respectively), the estimate for the between subject CV is assumed to be 38.1% for both parameters. The sample size calculation is based on log-transformed data and two, one-sided t-tests with 5% significance levels. 72 subjects will be randomized (12 to placebo [3/arm]). 60 of those subjects will be randomized to receive active AZD6140 in order to ensure at least 48 subjects receiving AZD6140 complete the study (this assumes a 20% withdrawal rate).

In the event that a significant interaction is detected and pooling across doses is not possible, there will be at least 99% power to show that the 90% confidence limits for the ratio (Japanese/Caucasian) of geometric mean will fall within the interval 50% to 200% (ruling out more than a dose doubling effect of ethnic group), if the hypothesis of equality is true.

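### The stated power of at least 90% is for one PK parameter in one analysis; the similarity rule requires both AUCss,tau and Css,max to pass, which has about 82–89% power at the planned 12 per arm

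*Supplement*

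**What the plan says.** Section 6.5 sets out the power calculation. It starts from the planned completers, "With 12 active evaluable subjects per arm in a factorial design", and claims that "the study has been planned to have at least 90% power to show that the 90% confidence limits" for the ratio of geometric means "will fall within the interval 70% to 143%, if the hypothesis of equality is true", provided dose and ethnic group do not interact. For variability, "the estimate for the between subject CV is assumed to be 38.1% for both parameters". The method is given as follows: "The sample size calculation is based on log-transformed data and two, one-sided t-tests with 5% significance levels". Sixty active subjects are randomized "in order to ensure at least 48 subjects receiving AZD6140 complete the study (this assumes a 20% withdrawal rate"). The section gives no correlation between the two parameters and no power for both passing together, and it does not mention the weight-adjusted analysis.

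Section 6.4(b) sets the decision rule. The primary PK parameters, AUCss,tau and Css,max, "with / without weight adjustment will be compared in a factorial design between the Japanese and Caucasian subjects". Similarity is concluded if the 90% intervals for both "are completely contained within the interval (0.7-1.43) for all comparisons". A later sentence adds that a BMI-adjusted comparison might be considered.

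**The concern.** The power statement and the rule describe different events. Section 6.5 uses one CV and one pair of one-sided tests, which is the calculation for one interval. Section 6.4(b) needs at least two intervals to pass, and four if its last phrase covers two parameters in two analyses. A rule that needs every interval to pass cannot have more power than its weakest component, and that component is planned at only just over 90%.

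What is at stake is how a failure would be read. If the rule fails, a reader who believes it had at least 90% power under equality will give the failure more weight as evidence of an ethnic difference than it deserves. The undefined scope adds to this: after the data are in, one person could say the rule was met on two intervals and another that it failed on four.

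**Working it through.** **Inputs from Section 6.5:** 12 evaluable active subjects per arm, so 24 per ethnic group with the two doses pooled; CV 38.1% for both parameters (the weighted mean for AUC in the earlier study was 37.8%); true ratio 1; limits 0.70 and 1.43; two one-sided 5% t-tests on the log scale.

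**Step 1: reproduce the plan's figure (one parameter, one analysis).**

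- Log-scale SD = √ln(1 + 0.381²) = 0.368.
- Standard error of the log ratio = 0.368 × √(2/24) = 0.1063.
- Log limits: ln 0.70 = −0.357 and ln 1.43 = +0.358.
- Normal approximation: 2Φ(0.357/0.1063 − 1.645) − 1 = 2Φ(1.71) − 1 ≈ 0.913.
- Exact calculation with the t critical value (1.679 on 45 df for a model with ethnic group and dose), integrating over the residual variance: **90.4%**. It is 90.4% on 44 df as well, and 90.9% at CV 37.8%.

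The dropout step also reproduces (48/0.8 = 60). So does the fallback: 99.5% power per dose for 50% to 200%, against the stated 99%. Nothing in Section 6.5 is miscalculated.

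**Step 2: bounds for both parameters passing, needing no correlation.** With each parameter at 90.4%:

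- It cannot exceed 90.4%, which is reached only if the two always pass or fail together.
- It cannot fall below 1 − 2 × (1 − 0.904) = 80.8%.
- If the two are independent it is 0.904² = 81.7%.

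**Step 3: joint power by assumed correlation.** The documents give no AUC–Cmax correlation, so a range is shown. The figures come from simulating correlated log-scale estimates and residual variances at true ratio 1 (600,000 trials per cell). The ranges cover CV 38.1% for both parameters, and 37.8% with 38.1%.

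| Within-group correlation | 24 per ethnic group (48 completers) | 30 per ethnic group (all 60 evaluable) |
|---|---|---|
| 0 | 81.8–82.2% | 92.4–92.7% |
| 0.5 | 83.1–83.5% | 92.9–93.1% |
| 0.8 | 85.5–85.9% | 93.9–94.1% |
| 0.95 | 87.9–88.2% | 95.0–95.1% |
| 0.99 | 89.2–89.5% | 95.6–95.8% |

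At the planned 48 completers the joint figure is below 90% at every correlation tried. It would reach 90% only very close to perfect correlation.

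**Step 4: sample size at which the joint rule reaches 90%.** About 28 evaluable per ethnic group at correlation 0, falling to about 26 at 0.95. Out of 30 randomized, that is withdrawal of 2/30 = 7% to 4/30 = 13%, against the assumed 20%.

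**Step 5: adding the weight-adjusted pair.** Requiring further intervals cannot raise the power. As an illustration, suppose the two groups have the same mean weight, weight correlates 0 or 0.3 in size with log exposure, and the two parameters correlate 0.5 to 0.95. All four intervals then pass in about 80–87% of simulated trials. These inputs are assumptions; only the direction follows from the plan.

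**The case against.** Several points on the other side are sound.

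- **The calculation is correct for what it computes.** Every figure in Section 6.5 reproduces. A reader might infer a sample-size error; there is none, only a mismatch between the power statement and the rule.
- **The shortfall is at the minimum sample.** With 60 active subjects randomized, two-parameter power is above 90% unless withdrawal exceeds about 7–13%. This limits the practical harm. But Section 6.5 makes its claim at 12 per arm, and the replacement trigger in Section 3.4.3 also uses 12, so the plan protects no higher number.
- **The phrase about all comparisons is ambiguous.** It may mean the two parameters, the doses if they cannot be pooled, or the adjusted and unadjusted analyses. The SAP, which Section 6.1 defers and which is not shown, may settle this. The two-parameter shortfall holds under any of these readings, because both parameters are named in the rule. A reader might also count the BMI analysis as a hurdle; that sentence stands after the rule and only says the analysis might be considered, so the text does not support it.
- **Type I error is safe.** Requiring every interval to pass cannot increase false conclusions of similarity.
- **The comparison is not the whole trial.** Section 2.1 sets objectives of investigating safety and PK, and Section 1.2 presents the ethnic comparison as a further aim. Calling this the rule that decides the trial would overstate it.

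A stronger reading is that lighter Japanese subjects would push the unadjusted ratio away from 1 and cut the power severely. It is true in principle that if weight differs and exposure depends on it, the adjusted and unadjusted ratios cannot both be 1. But the documents give neither a weight difference nor an exposure–weight relation. Section 3.3.2 applies the same BMI range and minimum weight to both groups, and Section 1.1 reports similar single-dose PK. No figure for such a loss can be drawn from the plan.

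**Conclusion.** The concern holds in a limited form. At 12 evaluable active subjects per arm, CV 38.1% and a true ratio of 1, power is 90.4% per parameter but about 82–89% for the AUCss,tau and Css,max rule in one analysis. The shortfall against the stated 90% is therefore about 1 to 8 points. Its size depends on the assumed correlation (0 to 0.99); its direction does not, short of near-perfect correlation. If the weight-adjusted intervals must pass too, power is no higher and probably lower, by an amount the documents do not allow one to fix.

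This is a statement to correct and a rule to define. It does not show that the trial is too small, and it does not undermine a conclusion of similarity if one is reached. It should be fixed, but the study could proceed safely without it.

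**What to change.** **Section 6.5:** restate the power as about 90% for each parameter and about 82–89% for both together at 12 evaluable per arm, naming the correlation assumed. The sponsor could take that correlation from the earlier multiple-dose study and quote one figure. It could also add that joint power is about 92–96% if all 60 active subjects are evaluable.

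**Section 6.4(b):** say which intervals must lie within 0.7–1.43. Either course is defensible:

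- name one analysis, unadjusted or weight-adjusted, as decisive for both parameters, and report the other as supportive; or
- keep both analyses in the rule and state the joint power of that rule, with its assumptions about weight.

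Say also that the BMI-adjusted comparison, if done, is outside the rule. Make the choice before PK results by ethnic group are seen; finalizing the SAP before database lock does not by itself ensure that, since Section 3.4.4.2 leaves the study open to the investigators.

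**Cost:** a few sentences and a slightly less favourable stated power. No more subjects, no new procedures and no change to the error rate.

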In the multiple ascending dose study D5130C05239, 1 subject had an increase in liver transaminases of more than 3 times the upper limit of normal after 4 daily doses of 300 mg

AZD6140, and was discontinued from the study. The transaminases returned to normal after 24 days. Another subject had a milder increase in transaminase after 4 twice-daily doses of 200 mg that improved despite continuation and increase in dose of AZD6140. There were no other laboratory findings, and no electrocardiogram (ECG), Holter monitor or vital signs findings of concern during any of the studies.

Study D5130C05266 was a study in healthy Japanese and Caucasian subjects to assess the safety and tolerability, as well as the pharmacokinetics and pharmacodynamics of single oral doses ranging from 50 mg to 600 mg of AZD6140. This study was conducted in the United States (US, Hawaii), with the requirement that Japanese subjects were to have both parents and 4 grandparents who were Japanese. Subjects in both ethnic groups tolerated the range of doses well. The pharmacokinetics of AZD6140 was similar in Japanese and Caucasian individuals following single oral administration of immediate release tablets in the range of 50 mg to 600 mg. After oral dosing, absorption of AZD6140 was rapid in both Japanese and Caucasians as evidenced by the 2 to 3 hour t_{max} . Mean C_{max} of AZD6140 increased linearly over the dose range of 50 mg to 600 mg in Japanese subjects but was linear only up to 400 mg in Caucasians. At the highest dose, 600 mg, C_{max} of AZD6140 seemed to plateau in Caucasians. Mean AUC increased linearly in both Japanese and Caucasian individuals up to 600 mg, with Caucasians exhibiting a slightly lower AUC at 600 mg; unlike C_{max} , mean AUC did not plateau in Caucasians. The mean $t_{1/2}$ of AZD6140 was around 8 to 12 hours in both races. The pharmacokinetics of the active metabolite, AR-C124910XX, was similar between Japanese and Caucasian individuals up to 400 mg. C_{max} and AUC of AR-C124910XX increased linearly over a dose range of 50 mg to 600 mg in Japanese but up to 400 mg in Caucasians. Both C_{max} and AUC values were about 30% lower in Caucasians compared to the Japanese at 600 mg. The platelet aggregation inhibition (PAI) response to AZD6140 was similar in Japanese and Caucasian individuals. Mean PAI greater than 90% was maintained for at least 12 hours at doses 200 mg or greater, with close to 100% inhibition at around t_{max} .

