The initial single dose of 100 mg (1.7 mg/kg/day, assuming the average body weight is 60 kg) on Day 1 of Cohort A in this study is 1/12th of the NOAEL (20 mg/kg/day) estimated in the 1-month oral toxicity study in rats and 1/120th of that (200 mg/kg/day) estimated in the 1-month study in marmosets. The second multiple dose of 300 mg bid (Cohort B), daily dose of 600 mg, is 1/2nd and 1/20th of the NOAELs, respectively. Although the chronic liver inflammation seen in 3-month studies in marmosets is considered the result of dosing trauma and not treatment-related, the treatment relationship of the other findings related to potential effects in the liver observed in preclinical and clinical studies conducted to date (increased ALP, ALT in 3-month studies in rats, and liver transaminase increases in the clinical multiple ascending dose study conducted in Europe, D5130C05239) is not well established. However, frequent monitoring (Days 1, 2, 4, 7, 10, 11, 13) of liver function laboratory tests is scheduled in this study, and the stopping criteria for ALT and AST is specified, such that if these observations are related to effects of ADZ6140 in the liver in the clinic, the effects will be detected at the earliest opportunity and stopping criteria is set adequately. Therefore, the safety of subjects in this study will be ensured.

In a multiple dose study in Caucasians (D5130C05239), the results in the 50 mg twice daily dosing group showed that the mean AUC_t for AZD6140 and AR-C124910XX at steady state were about 1.8 and 1.9 times higher than those after single administration of the same dose, respectively. The results from the single dose study in Japanese and Caucasians (D5130C5266) showed approximate linearity of pharmacokinetic parameters of plasma concentrations of AZD6140 and AR-C124910XX with increasing dose in the range of 50 to 600 mg of AZD6140 in Japanese subjects. These results indicate that in Japanese subjects, AUC_t and C_{max} at steady state following 300 mg bid should not exceed those for a single 600 mg dose for which good tolerability has been shown. In Caucasians, the safety of repeatedly administered AZD6140 of up to 600 mg has also been demonstrated.

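### Pooling over dose rests on an interaction test with about 38% to 50% power, and the 99% by-dose power in 6.5 is for limits that 6.4 does not use

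*Supplement*

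**What the plan says.** Section 6.4(b) compares AUCss,τ and Css,max between Japanese and Caucasian subjects in a factorial design, "adjusting for dose level if appropriate (no significant interaction between dose and ethnic group". The level of the interaction test is not given. Similarity is concluded if the 90% CIs for the AZD6140 geometric mean ratios lie wholly within 0.7-1.43, and this is to hold for every comparison. It is the only acceptance rule in the protocol.

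Section 6.5 sizes the study on "two, one-sided t-tests with 5% significance levels". For the pooled comparison, "the study has been planned to have at least 90% power" against 70%-143%, "if the hypothesis of equality is true assuming that there is no significant" interaction. For the other case it says "In the event that a significant interaction is detected and pooling across doses is not possible, there will be at least 99% power" that the 90% limits "will fall within the interval 50% to 200% (ruling out more than a dose doubling effect of ethnic group"), again under equality. It does not say what would be concluded from a result inside 50%-200%.

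**The concern.** Two things do not fit together.

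First, a non-significant interaction is treated as licence to pool, although the study is not sized to detect one. If the ethnic ratio differed at 300 mg but not at 100 mg, the pooled ratio would average the two. A pass could then be read as similar exposure at the higher dose, which was not shown.

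Second, 6.5 reassures the reader that the by-dose analysis is amply powered, but against limits that 6.4 never mentions. Comparing the ethnic groups is a stated aim in section 1.2, so a reader needs to know what the study can show at each dose.

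**Working it through.** **Inputs (section 6.5).** CV 38.1%; 12 evaluable active subjects per ethnic group and dose; two one-sided 5% t-tests on the log scale; true ratio 1 for the power figures. The interaction test level is not stated, so I assume 5% and 10%. The log SD is √ln(1 + 0.381²) = 0.368.

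**The plan's own figures.** The values in brackets are quick normal approximations; the final values integrate over the estimated SD.
- Pooled, 24 v 24, limits 0.70-1.43: SE = 0.368 × √(2/24) = 0.1063. The CI half-width is about 1.680 × 0.1063 = 0.1786. The estimate must lie within 0.3567 − 0.1786 = 0.178 of zero, or 1.68 SE (about 0.91). Exact power 0.904, so the stated 90% reproduces.
- By dose, 12 v 12, limits 0.50-2.00: SE = 0.368 × √(2/12) = 0.1503. The half-width is 1.717 × 0.1503 = 0.258 (22 df). The margin is 0.693 − 0.258 = 0.435, or 2.89 SE. Exact power 0.995 (22 df) or 0.996 (44 df), so the stated 99% reproduces.

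**By-dose power on 6.4's limits.** For 0.70-1.43 the margin falls to 0.357 − 0.258 = 0.099, or 0.66 SE. Exact power is 0.49 (22 df) to 0.51 (44 df) per dose, and about 0.27-0.28 for both doses. With all 15 per cell evaluable it is about 0.66 per dose and 0.46 for both.

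**Power of the interaction test.** SE of the difference in log ratios = 0.368 × √(4/12) = 0.2126, with 44 df. For ratios 1.00 and 1.43 the difference is ln 1.43 = 0.358, or 1.68 SE.

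| Ratio of ratios | 5% level | 10% level |
|---|---|---|
| 1.3 | 23% | 34% |
| 1.43 | 38% | 50% |
| 1.6 | 58% | 70% |
| 2.0 | 89% | 94% |

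**The two-stage rule at 1.00 (100 mg) and 1.43 (300 mg).** The dose-averaged ratio is √(1.00 × 1.43) = 1.196. Simulation (400,000 trials per scenario, one parameter, 12 per cell, both doses required to pass when not pooled) gives:

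| Outcome | Test at 5% | Test at 10% |
|---|---|---|
| No significant interaction, pooled CI inside 0.7-1.43 | 31% | 24% |
| Significant interaction, both doses inside 0.7-1.43 | about 0% | about 0% |
| Significant interaction, both doses inside 0.5-2.0 | 17% | 26% |
| Total if 0.5-2.0 were the by-dose criterion | 48% | 51% |

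With both AUCss,τ and Css,max in this scenario, 0.7-1.43 kept throughout and an assumed correlation of 0.6 to 0.9, the claim rate is 17-23% (5% level) or 12-18% (10% level). If both doses had to meet 0.7-1.43 with no gate, it would be about 2.7% for one parameter.

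**The case against.** **The limits do not clearly widen.** A reader might infer that the criterion loosens to 50%-200% once an interaction is found. The documents do not say so. That interval stands only in a power statement, with its own weaker meaning, and 6.4 keeps 0.7-1.43 throughout. This stands: the 17-26% share and the 48-51% total hold only if the interval was meant as an acceptance rule, in which case 6.4 and 6.5 conflict.

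**A pooled pass at 1.00/1.43 is not a type I error.** The pooled test concerns the average ratio, 1.196, which is inside the limits. Setting 31% against a nominal 5% would compare different estimands. This also stands. The fault lies in what a reader may take the pass to mean at 300 mg.

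**The documents do not predict a ratio of 1.43 at 300 mg.** It is tempting to infer one from section 1.1, where metabolite Cmax and AUC "values were about 30% lower in Caucasians compared to the Japanese at 600 mg" and parent Cmax seemed to level off at that dose in Caucasians. But the criterion concerns the parent. Its AUC did not plateau and was only slightly lower in Caucasians, its Cmax was linear up to 400 mg, and multiple-dose PK was approximately linear in the European study. Section 3.2 says only that in Japanese subjects exposure "at steady state following 300 mg bid should not exceed those for a single 600 mg dose". The scenario is illustrative.

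**Some protection exists.** Section 6.4 already summarises PK by treatment and ethnic group, so a difference at 300 mg would be visible, and the SAP, which is not among the documents, may set the test level. But descriptive summaries give no by-dose ratio with its CI, and the gate and both intervals are in the protocol itself. Quoting power at equality is conventional and not a fault.

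**Conclusion.** The concern holds in limited form. The interaction test is too weak for its non-significance to support reading a pooled result as similarity at each dose: power is about 38% (5% level) or 50% (10% level) against a difference between doses as large as the similarity limit. In that scenario a pooled pass occurs in about 31% (24%) of trials for one parameter, and less often when both must pass. It supports similarity on average over 100 mg and 300 mg, and no more.

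The at-least-99% figure is arithmetically right but answers a question that 6.4 does not ask. On 6.4's limits, by-dose power is about 50% per dose and 27-28% for both doses.

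These figures assume CV 38.1%, 12 per cell, a common variance, a true 100 mg ratio of 1.00 in the two-stage scenario, and an interaction level of 5% or 10%. This is a moderate point about interpretation and a mismatched power statement. It does not show that the pooled test is invalid.

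**What to change.** 1. In 6.4, report the ratio and 90% CI at each dose for AZD6140 AUCss,τ and Css,max from the factorial model with interaction, whatever the interaction test shows, beside the pooled ratio.
2. State that a pooled pass supports similarity on average over the two doses only.
3. State that 0.7-1.43 applies to the by-dose comparisons, and label 50%-200% as descriptive only.
4. In 6.5, restate by-dose power against 0.7-1.43 as about 50% per dose.

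The cost is protocol and SAP wording, two extra estimates per parameter and a less favourable stated power. No subjects or procedures are added. By the pooled calculation above, 90% power at each dose would need about 24 evaluable subjects per ethnic group and dose, which this fix does not ask for. The same ratios for AR-C124910XX would be useful but are optional and not part of the error.
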